6.3. Measures to Minimize Bias: Randomization and Blinding

6.3.1. Randomization and Stratification

All participants will be randomized on Day 1 using a centralized interactive response technology (IRT) after the Investigator has verified that they are eligible to participate in the study. After Screening, eligible participants will be assigned to a treatment arm by stratified randomization. For each disease cohort, participants meeting eligibility criteria will be randomly assigned in a 3:1:3 ratio to receive ALXN2050 180 mg bid, ALXN2050 120 mg bid, or placebo bid, respectively (Table 8) during the Blinded Initial Evaluation Period. The LN cohort will continue with the same treatment allocation during the Blinded Extended Treatment Period. For the IgAN cohort, participants assigned to the placebo group will also be assigned to their active study treatment for the Blinded Extended Treatment Period (ALXN2050 120 mg bid or ALXN2050 180 mg bid) in a 1:1 allocation ratio at the time of initial randomization.

The randomization stratum for the LN cohort is as follows:

 Corticosteroid induction treatment initiated (prior to screening, during Screening Period)

The randomization stratum for the IgAN cohort is as follows:

Mean proteinuria from 2 valid 24-hour urine collections (1 to 2 g/day versus > 2 g/day)

6.3.2. Blinding

All investigational site personnel, other staff directly associated with the conduct of the study, and all participants will be blinded to treatment assignment during the Blinded Initial Evaluation Period and the Blinded Extended Treatment Period. The double-blind will be maintained by using identical study treatment kits and labels for all participants. The placebo tablet will have an identical appearance to that of ALXN2050. The randomization code will be maintained by the IRT provider. Select Alexion staff will be unblinded for the primary analysis at Week 26. All participants, Investigators, and site personnel will remain blinded to treatment assignment from Day 1 through the end of the Blinded Extended Treatment Period (ie, Week 50). After completion of all assessments at the end of the Blinded Extended Treatment Period, participants will begin receiving open-label treatment during the OLE Period and therefore, participants, Investigators, and site personnel will no longer be blinded to the initial treatment assignment. Knowledge of the initial treatment assignment during the OLE Period is not expected to impact the data integrity as the primary and key secondary endpoints have already been collected and due to the objective nature of these endpoints.

6.3.3. Unblinding

During the Blinded Initial Evaluation Period and the Blinded Extended Treatment Period, unblinding should only be considered for the safety of the participant. In case of an emergency, the Investigator has the sole responsibility for determining if unblinding of a patient's intervention assignment is warranted. Participant safety must always be the first consideration in making such a determination. If the Investigator decides that unblinding is warranted, the Investigator will be able to unblind the participant's treatment allocation directly using the IRT. If a participant's intervention assignment is unblinded, the Sponsor must be notified within

24 hours after breaking the blind. The date and reason that the blind was broken must be recorded in the source documentation.

In the event of a suspected unexpected serious adverse reaction (SUSAR), the blind will be broken for that specific participant only. The blind will be maintained for persons responsible for the ongoing conduct of the study (eg, monitors, Investigators) and those responsible for data analysis and interpretation of results, such as biometrics personnel.

Unblinded information will only be accessible to those who are involved in safety reporting to Health Authorities, IECs, and/or IRBs.

Any participant who is unblinded during the blinded periods will be withdrawn from the study.

Investigators will receive only blinded information unless unblinded information is judged necessary for safety reasons.

6.4. Study Intervention Compliance

When participants are dosed at the investigational site, they will receive study intervention directly from the Investigator or designee, under medical supervision. The date and time of each dose administered in the clinic will be recorded in the source documents and in the eCRF.

When participants self-administer study intervention at home, compliance with the study intervention will be assessed by direct questioning and counting of returned tablets during the next in-clinic visit and recorded in the source documents. Deviation(s) from the prescribed dosage regimen should be recorded.

A record of the quantity of study intervention dispensed and administered to/taken by each participant must be maintained and reconciled with study intervention records provided to the investigational site. Intervention start and stop dates, including dates for planned and unplanned intervention delays and/or dose reductions will also be recorded.

6.5. Prior and Concomitant Therapy

Any medication (including over-the-counter or prescription medicines, vitamins, and/or herbal supplements), vaccines, or other specific categories of interest that the participant is receiving at the time of enrollment or receives during the study must be recorded along with:

- Reason for use
- Dates of administration, including start and end dates
- Dosage information including dose and frequency

Nonpharmacologic treatments and therapies that the participant receives during the clinical study must be recorded along with:

- Reason for use
- Dates of administration, including start and end dates
- Diagnostics administered, if applicable
- Whether the treatment is ongoing

The Medical Monitor should be contacted if there are any questions regarding concomitant or prior therapy.

6.5.1. Allowed Medications and Therapy

Allowed concomitant therapy is discussed in Section 6.5.3.1 (LN cohort) and Section 6.5.3.2 (IgAN cohort).

Any medication or therapy (including over-the-counter or prescription medicines, vaccines, vitamins, and/or herbal supplements) deemed necessary for the participant's care during the study, or for the treatment of any AE, along with any other medications, other than those listed as disallowed medications in Section 6.5.2, may be given at the discretion of the Investigator. However, it is the responsibility of the Investigator to ensure that details regarding the medication are recorded on the eCRF (Section 8.2.5).

If adequate blood pressure control is not achieved during the study, participants may receive additional antihypertensive agents, but not agents that affect proteinuria during the study through Week 50. It is recommended that nonsteroidal anti-inflammatory drugs (NSAIDs) not be initiated during the study due to the possibility of adverse effects on renal function. However, these can be used if indicated for symptomatic relief for a short period of time (up to a maximum of 7 days per the labeled usage; if an increased dose/treatment duration is required, the Investigator must discuss with the Sponsor).

For participants in the LN cohort only:

- Pneumocystis pneumonia prophylaxis is allowed at the discretion of the Investigator.
- Treatment with antimalarial agents such as hydroxychloroquine are strongly recommended unless contraindicated.
- Measures to prevent and treat osteoporosis are encouraged during the study; these
 measures may include any, or all, of the following: calcium carbonate or citrate,
 Vitamin D, and bisphosphonates.
- Immunosuppressive drugs for additional standard of care therapy are allowed.

6.5.2. Disallowed Medications and Therapy

Participants in both cohorts are prohibited from receiving any of the following medications and therapies during the entire duration of study participation:

- Experimental interventions or therapies
- A complement inhibitor (eg, eculizumab, ravulizumab)
- New use or modification of the dose of SGLT-2 inhibitors (up to 50 weeks)
- New use or modification of the dose of RAS inhibitor or direct renin antagonist treatment (up to 50 weeks)
- Known CYP3A sensitive substrates, moderate or strong CYP3A inducers, and/or moderate or strong CYP3A inhibitors are prohibited throughout the study, until 1 week after the final administration of study intervention (see Section 10.16 for a full list of these medications)

- Selected medications known to lower the seizure threshold and/or cause seizure should not be taken concomitantly (see Section 10.15 for a full list of these medications)
- Medications known to significantly prolong the corrected QT interval (QTc), with the exception of hydroxychloroquine in patients with LN

In the event that a participant receives a prohibited medication and/or therapy, the Investigator will consider the discontinuation of study intervention (Section 7.1). SGLT-2 inhibitors, RAS inhibitors, and direct renin antagonists are prohibited but may be considered without discontinuation of study intervention based on the discussion and approval of the Investigator and Medical Monitor.

Participants in the IgAN cohort are also prohibited from receiving any of the following medications and therapies during the entire duration of study participation:

- Hydroxychloroquine
- Immunosuppressive agents (eg, MMF)
- Systemic corticosteroids for > 14 consecutive days (short-term steroid course for ≤ 14 days for medical conditions not related to IgAN or surgery are permitted)

For participants in the LN cohort, escalation of immunosuppression is allowed for protocol-defined Renal, Extrarenal Flares, and Suboptimal Response (after Week 26). CNIs including, but not limited to voclosporin, are prohibited. If a CNI is used as additional standard of care therapy per the clinical judgment of the Investigator, ALXN2050 will need to be discontinued 3 days prior to CNI administration. However, the participant can remain in the study and continue the study visits as per the SoA.

Any medications not specified in this section, that remain a concern to the Investigator should be discussed with the Medical Monitor.

6.5.3. Allowed Concomitant Therapy

The allowed concomitant therapy consistent with the standard of care employed in this protocol are consistent with clinical studies in patients with LN (Rovin, 2019) and IgAN (Rauen, 2015).

6.5.3.1. Allowed Concomitant Therapy for LN Cohort

During the course of the study, participants in the LN cohort will receive allowed concomitant therapy consistent with the standard of care for induction and maintenance treatment of LN.

- For participants who have not started corticosteroid induction treatment prior to Screening:
 - Participants will receive a cumulative dose of 1 g of methylprednisolone IV administered in 1 or multiple divided doses or oral equivalent during the Screening Period (prior to Day 1).
 - During the Screening Period and no later than Day 2, all participants will receive oral corticosteroids with prednisone or prednisone equivalent with starting doses as outlined in Table 12. The starting minimum and maximum doses allowed are

- 30 mg/day and 60 mg/day, respectively. A corticosteroid taper will commence at Week 2 (Day 14). From Week 12 to Week 26, the target dose is 7.5 mg/day. Following Week 26, participants may remain on 7.5 mg/day or continue to taper at the clinical discretion of the Investigator until Week 46. From Week 46 to Week 50, the dose of corticosteroids must not be changed.
- During the Screening Period and no later than Day 1, participants will receive a cumulative dose of 1 to 1.5 g/day of MMF any time after completion of the IV methylprednisolone during the Screening Period and no later than Day 1. The dose can be administered in multiple divided doses. Participants will continue to receive 1 to 1.5 g/day for 1 week.
- After receiving 1 to 1.5 g/day for 1 week, the dose will be titrated per the discretion of the Investigator to a cumulative dose up to 3 g/day of MMF no later than by Week 4 (Day 28). The dose can be administered in multiple divided doses. Participants will continue to receive 1.5 to 3 g/day of MMF until Week 50, after which it may be decreased or discontinued based on the Investigators' judgment and the KDIGO clinical practice guidelines (KDIGO, 2012).
- For participants who have initiated corticosteroid induction treatment prior to Screening and do not meet Exclusion Criterion 28 (Section 5.2):
 - If the participant already received methylprednisolone IV ≥ 1 g or equivalent oral corticosteroid induction and is receiving MMF ≥ 2 g/day prior to Screening, then methylprednisolone IV will not be given. The participant may continue the current MMF dose during Screening, and during the Blinded Initial Evaluation Period the dose of MMF should be adjusted to achieve 1.5 to 3 g/day no later than Day 28 (Week 4). MMF will be continued at 1.5 to 3 g/day until Week 50, after which it may be decreased or discontinued based on the Investigator's judgment and the KDIGO clinical practice guidelines (KDIGO, 2012).
 - If the participant already received methylprednisolone IV ≥ 1 g or equivalent oral corticosteroid induction and is receiving MMF < 2 g/day prior to Screening, then methylprednisolone IV will not be given, and the MMF dose will be increased during the Screening Period (no later than Day 1) to a cumulative dose of 1 to 1.5 g/day. Participants will continue to receive 1 to 1.5 g/day for 1 week, after which the MMF dose will be increased per the discretion of the Investigator to 1.5 to 3 g/day to be achieved no later than Week 4 (Day 28). These doses can be administered in multiple divided doses. Participants will continue to receive 1.5 to 3 g/day until Week 50, after which it may be decreased or discontinued based on the Investigator's judgment and the KDIGO clinical practice guidelines (KDIGO, 2012).

 - If a participant is already receiving prednisone or prednisone equivalent, the dose will be continued until Day 2, at which time prednisone or prednisone equivalent should be administered (the minimum and maximum doses allowed are 30 mg/day and 60 mg/day, respectively) as outlined in Table 12. The prednisone dose will be tapered starting at Week 2 (Day 14) according to the schedule. From Week 12 to Week 26, the target dose is 7.5 mg/day. Following Week 26,

participants may remain on 7.5 mg/day or continue to taper at the clinical discretion of the Investigator until Week 46. From Week 46 to Week 50, the dose of corticosteroids must not be changed.

Table 12: Corticosteroid Taper for Participants with Lupus Nephritis

Study Week	Prednisone Dose or Equivalent Dose (mg/day)			
	≤ 60 kg	61 to 80 kg	81 to 100 kg	≥ 100 kg
Screening to Week 2ª	30	40	50	60
2	25	35	40	50
4	25	30	30	40
6	20	25	20	30
8	15	20	15	20
10	10	15	10	10
12 ^b	7.5	7.5	7.5	7.5

^a Weight at Screening will be used for dosing, and this weight category will be used throughout the study. The minimum and maximum starting doses of prednisone are 30 mg and 60 mg, respectively.

- An equivalent dose of enteric-coated mycophenolic acid sodium (MPS) may be used instead of MMF (ie, a 360 mg dose MPS is equivalent to a 500 mg dose of MMF).
- Investigators may adjust the dosage of MMF due to tolerance or AEs. If the
 participant's symptoms resolve, the Investigator should attempt to increase MMF (or
 equivalent) to the goal level of 1.5 to 3 g/day. If symptoms return, then the participant
 should be continued on the highest tolerable dose.
- Changes to the dose of MMF and the justification will be documented in the eCRF.

Other considerations regarding the corticosteroid taper:

- All participants will have a scheduled corticosteroid taper starting on Day 14.
 Participants will reduce their prednisone dose according to their baseline body weight
 over 10 weeks until the dose is 7.5 mg/day by Week 12 (Table 12). From Week 12 to
 Week 26, the target dose is 7.5 mg/day. Following Week 26, participants may remain
 on 7.5 mg/day or continue to taper at the clinical discretion of the Investigator until
 Week 46. From Week 46 to Week 50, the dose of corticosteroids must not be
 changed.
- Deviations from the scheduled corticosteroid taper for any reason other than Renal Flare or Extrarenal SLE Flare will confound interpretation, so every attempt should be made to adhere to the tapering schedule.
- If disease is too clinically active in the opinion of the Investigator to begin the
 corticosteroid taper after Week 2, then the participant may continue to receive his or

b From Week 12 to Week 26, the target dose is 7.5 mg/day. Following Week 26, participants may remain on 7.5 mg/day or continue to taper at the clinical discretion of the Investigator until Week 46. From Week 46 to Week 50, the dose of corticosteroids must not be changed.

her initial corticosteroid dose for up to an additional 28 days. Similarly, participants who have started the taper and whose disease is too clinically active to continue tapering may remain at the same taper dose achieved for up to an additional 28 days. Failure to achieve the corticosteroid taper by Week 12 will not be considered as Treatment Failure and will be captured as a secondary endpoint.

 However, the prednisone dose may NOT be increased beyond the taper dose achieved unless the participant meets the protocol-defined criteria for Renal Flare (Section 8.1.6) and/or severe Extrarenal SLE Flare (Section 8.1.7), in which case these participants will receive additional standard of care therapy and will be included as treatment failures.

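### For LN participants with prior steroid induction on MMF of 1.5 to below 2 g/day, the protocol orders an increase to 1 to 1.5 g/day; none is possible, and above 1.5 g/day every permitted target is a cut

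*Protocol*

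**What the plan says.** Protocol Section 6.5.3.1 deals with LN participants who began corticosteroid induction before Screening. Those who have already had at least 1 g of intravenous methylprednisolone, or an oral equivalent, are split by their MMF dose:

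- At 2 g/day or more: "The participant may continue the current MMF dose during Screening". The dose is then brought within 1.5 to 3 g/day by Day 28.
- If the participant "is receiving MMF < 2 g/day prior to Screening", the instruction is that "the MMF dose will be increased during the Screening Period (no later than Day 1) to a cumulative dose of 1 to 1.5 g/day". The next step reads: "Participants will continue to receive 1 to 1.5 g/day for 1 week, after which the MMF dose will be increased per the discretion". That later increase is left to the investigator and must reach 1.5 to 3 g/day by Week 4.

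The same section names 1.5 to 3 g/day as the goal and equates 500 mg of MMF with 360 mg of mycophenolic acid sodium (MPS). On departures it says: "Investigators may adjust the dosage of MMF due to tolerance or AEs". On records it says: "Changes to the dose of MMF and the justification will be documented in the eCRF". Section 6.5 adds: "The Medical Monitor should be contacted if there are any questions regarding concomitant or prior therapy".

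Exclusion Criterion 28d (Section 5.2.2) removes participants on more than 2 g/day for eight or more consecutive weeks. It does not reach anyone below 2 g/day.

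**The concern.** The lower branch admits any dose below 2 g/day, but its target stops at 1.5 g/day. For a participant between those two values the verb and the number disagree. The site must ignore the verb, ignore the number, or ask the Medical Monitor.

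If the number is obeyed, a participant with clinically active LN (required by Section 5.1.2), whose dose already lies within the goal range, has background immunosuppression lowered without any tolerability reason. A participant at 2 g/day keeps the full dose. What is at stake is a rule that can be followed, and the avoidance of a reduction that the wording suggests was not intended.

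**Working it through.** The plan gives no figure to reproduce, so the check is one of ranges.

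**Inputs, all from Protocol Section 6.5.3.1.** Let d be the current MMF dose and t the target. The lower branch covers d < 2 g/day. It sets t between 1 and 1.5 g/day and calls the change an increase, so t must exceed d.

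| d (g/day) | Targets in 1 to 1.5 that exceed d | Can the rule be followed? |
|---|---|---|
| d < 1 | 1 to 1.5 | Yes |
| 1 ≤ d < 1.5 | Those above d, up to 1.5 | Yes, in part of the range |
| d = 1.5 | None | Not as an increase; holding 1.5 meets the number |
| 1.5 < d < 2 | None; every t is below d | No; the number can be met only by a cut |

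**Who could be in the last row.** The documents give no dose distribution, so this rests on an assumption about dose steps. In 500 mg units, nobody lies strictly between 1.5 and 2 g/day. In 250 mg half-units, 1.75 g/day is the only dose affected. In MPS terms:

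- 1.5 g is 3 × 360 = 1080 mg
- 1.75 g is 3.5 × 360 = 1260 mg
- 2 g is 4 × 360 = 1440 mg

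**Size at an assumed 1.75 g/day.**

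- Smallest cut that satisfies the number: 1.75 − 1.5 = 0.25 g/day, and 0.25/1.75 = 14%.
- Largest cut permitted: 1.75 − 1 = 0.75 g/day, and 0.75/1.75 = 43%.
- Over the stated one-week hold: 7 × 0.25 = 1.75 g to 7 × 0.75 = 5.25 g.
- Against 26 weeks (182 days) at 1.5 to 3 g/day, which is 273 to 546 g: 1.75/546 = 0.3% to 5.25/273 = 1.9%.

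The seven-day figures are not an upper bound. The step may begin during Screening, and the return to 1.5 to 3 g/day is due only by Week 4. If the step began on Day 1 and lasted 28 days, the shortfall would be 28 × 0.25 = 7 g to 28 × 0.75 = 21 g, or 7/546 = 1.3% to 21/273 = 7.7%. A start during Screening would add to the days at the lower dose.

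**Check of the fix.** With the cut-off at 1.5 g/day, every d in the lower branch satisfies d < 1.5, so at least one target between 1 and 1.5 g/day exceeds it. Every d of 1.5 g/day or more may continue and already meets the lower end of the goal range.

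**The case against.** The case against giving this much weight is strong, and most of it stands.

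- **No affected participant is shown.** The only MMF unit in the equivalence is 500 mg, and on that step the band above 1.5 and below 2 g/day is empty. This stands, and it caps the severity.
- **The harm can be small.** A site can satisfy the number with 1.5 g/day, which is within the goal. This stands. A reader might infer that the rule forces a 43% cut, but nothing requires a dose below 1.5 g/day; the larger cut is only permitted.
- **Investigators have room to act.** A reader might infer that tolerance and adverse events are the sole grounds for changing MMF, so that keeping the current dose is barred. The text names those grounds without calling them exclusive, and it sends questions to the Medical Monitor. This also stands. Still, a query route and an eCRF record do not correct the rule.
- **The verb may be the slip.** Section 6.5.3.1 also starts participants without prior steroid induction on 1 to 1.5 g/day, so that range could be a deliberate common step. If so, replacing *increased* with *adjusted* would be enough. The documents do not say which was meant. Against this reading, the next branch lets participants at 2 g/day or more keep their dose, and a one-word edit would leave a dose already at goal being lowered and then raised again.

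None of this makes the verb and the number compatible, and I found no other text in the protocol or SAP that does.

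**Conclusion.** Wrong as written; minor. The contradiction is certain for doses above 1.5 and below 2 g/day, and at exactly 1.5 g/day the ordered increase is impossible although no cut is forced. At an assumed 1.75 g/day, the forced cut is at least 14% and the permitted cut is 43%, for at least one week. How many participants are affected is unknown and may be none.

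Three further inferences are not supported:

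- **Bias in the Week 26 comparison.** The rule is the same in all arms, assignment is randomised and blinded, steroid timing is a stratification factor, and 1.5 to 3 g/day is due 22 weeks (26 − 4) before the endpoint visit. The effect is negligible.
- **Loss from the Per-Protocol Set.** SAP Section 3 requires appropriate allowed concomitant therapy, and this rule leaves it unclear whether holding or lowering the dose is appropriate. Nothing says that either choice would exclude a participant.
- **The same fault for participants without prior steroid induction.** Their instructions do not describe the first MMF step as an increase, so this point makes no claim about them.

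**What to change.** In the two pre-treated branches of Protocol Section 6.5.3.1, move the cut-off from 2 to 1.5 g/day:

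- First branch: MMF of 1.5 g/day or more (MPS of 1080 mg/day or more) before Screening. The current dose may continue during Screening, with adjustment within 1.5 to 3 g/day by Week 4 as now.
- Second branch: MMF below 1.5 g/day (MPS below 1080 mg/day) before Screening. The step to 1 to 1.5 g/day is unchanged.

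Equivalently, keep the present layout and add that participants already on 1.5 g/day or more may continue their dose during Screening, with the same later adjustment.

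The cost is two cut-off values, or one sentence, in the next amendment. Exclusion Criterion 28d, the instructions for participants without prior steroid induction, data collection and the analysis all stay as they are. Whether the change counts as a substantial amendment under Protocol Section 10.1.1 is for the sponsor to decide. SAP Section 1 reports that screening and enrollment have been paused since 06 Sep 2024, so the change helps only future enrollees and should be in place before enrollment resumes.
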